**Annex 2. Participants Tracking Form**

**Name-Surname:**

**Date:**

**Tel Number:**

**Birth Date:**

**Age:**

**Sex:**

**Height:**

**Weight:**

**Dominant Side (Mark): Right / Left**

**Effected Side (Mark): Right/ Left**

**How did the problem occur? (Please explain):**

**Did you have any operation? Please write, if you did:**

**Do you have any additional problem?**

**No:**

**Yes/ If yes, What is it?**

**Assessment of Pain - Visual Analogue Scale**

- How severe is your shoulder pain during activity?

0.....5.....10  
(no pain) (worst possible pain)

- How severe is your shoulder pain during rest?

0.....5.....10  
(no pain) (worst possible pain)

### Assessment of Range of Motion and Muscle Strength

	Muscle Strength				Range of Motion						
	R		L		R			L			
	1	2	1	2	1	2	3	1	2	3	
Shoulder Flexion											
Shoulder Extension											
Shoulder Abduction											
Shoulder Adduction											
Shoulder IR											
Shoulder ER											
Elbow Flexion											
Elbow Extension											
Supination											
Pronation											

## Assesment of Disability - Disabilities of the Arm, Shoulder and Hand Questionnaire– DASH

### DISABILITIES OF THE ARM, SHOULDER AND HAND – British English

Please rate your ability to do the following activities in the last week by circling the number below the appropriate response.

	NO	MILD	MODERATE	SEVERE	UNABLE
	DIFFICULTY	DIFFICULTY	DIFFICULTY	DIFFICULTY	
1 Open a tight or new jar	1	2	3	4	5
2 Write	1	2	3	4	5
3 Turn a key	1	2	3	4	5
4 Prepare a meal.	1	2	3	4	5
5 Push open a heavy door	1	2	3	4	5
6 Place an object on a shelf above your head	1	2	3	4	5
7 Do heavy household jobs (e.g. wash windows, clean floors)	1	2	3	4	5
8 Garden or outdoor property work	1	2	3	4	5
9 Make a bed	1	2	3	4	5
10 Carry a shopping bag or briefcase	1	2	3	4	5
11 Carry a heavy object (over 10 lbs/ 5kgs)	1	2	3	4	5
12 Change a lightbulb overhead	1	2	3	4	5
13 Wash or blow dry your hair	1	2	3	4	5
14 Wash your back	1	2	3	4	5
15 Put on a jumper	1	2	3	4	5
16 Use a knife to cut food	1	2	3	4	5
17 Recreational activities which require little effort (e.g. card playing, knitting, etc)	1	2	3	4	5
17 Recreational activities which require you to take some force or impact through your arm, shoulder or hand (e.g. golf, hammering, tennis etc)	1	2	3	4	5
18 Recreational activities in which you move your arm freely (e.g. playing Frisbee, badminton etc)	1	2	3	4	5
20 Manage transport needs (getting from one place to another)	1	2	3	4	5
21 Sexual activities	1	2	3	4	5

	NOT AT ALL	SLIGHTLY	MODERATELY	Quite a bit	Extremely
22 During the past week, to what extent has your arm, shoulder or hand problem interfered with your normal social activities with family, friends, neighbours or groups? (circle number)	1	2	3	4	5

	NOT LIMITED AT ALL	SLIGHTLY LIMITED	MODERATELY LIMITED	VERY LIMITED	UNABLE
23 During the past week, were you limited in your work or other regular daily activities as a result of your arm, shoulder or hand problem? (circle number)	1	2	3	4	5

Please rate the severity of the following symptoms in the last week (circle number)	NONE	MILD	MODERATE	SEVERE	EXTREME
24 Arm, shoulder or hand pain	1	2	3	4	5
25 Arm, shoulder or hand pain when you do any specific activity	1	2	3	4	5
26 Tingling (pins and needles) in your arm, shoulder or hand	1	2	3	4	5
27 Weakness in your arm, shoulder or hand	1	2	3	4	5
28 Stiffness in your arm, shoulder or hand	1	2	3	4	5

	NO DIFFICULTY	MILD DIFFICULTY	MODERATE DIFFICULTY	SEVERE DIFFICULTY	SO MUCH DIFFICULTY THAT I CAN'T SLEEP
29 During the past week, how much difficulty have you had sleeping because of the pain in your arm, shoulder or hand? (circle number)	1	2	3	4	5

	STRONGLY DISAGREE	DISAGREE	NEITHER AGREE OR DISAGREE	AGREE	STRONGLY AGREE
30 I feel less capable, less confident or less useful because of my arm, shoulder or hand problem (circle number)	1	2	3	4	5

DASH DISABILITY/SYMP TOM SCORE =  $\frac{((\text{sum of n responses})-1)}{n} \times 25$  (where n is the number of completed responses)

A DASH score may not be calculated if there are greater than 3 missing items.

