### Evaluations

A Physiotherapist will applying the following evaluation parameters at the baseline, and at the end of 4-weeks treatment program, the same physiotherapist will be applying evaluation parameters. Primary outcome measures and applied evaluations are shown in Table 1.

**Table 1.** Primary outcome measures and evaluation methods

Primary Outcome Measures	Evaluation Methods
Range of Motion (ROM)	Goniometer
Pain	Visual Analogue Scale (VAS)
Disability	The Disabilities of the Arm, Shoulder and Hand (DASH) Questionnaire
Quality of Shoulder Function	Constant-Murley Score
Muscle Strength	Dynamometer
Pain Threshold	Algometer
Proprioception	Marmara Visual Auditory Joint Education Device (MarvaJED)
Kinesiophobia	Tampa Kinesiophobia Scale (TKS)
Satisfaction of the Treatment	Visual Analogue Scale (VAS)

The range of motion will be defined with ‘goniometer’, the pain with ‘Visual Analogue Scale (VAS)’, the disability with ‘The Disabilities of the Arm, Shoulder and Hand (DASH) Questionnaire’, the quality of shoulder function with ‘Constant- Murley Score’, the muscle strength with ‘dynamometer’, the pain threshold with algometer, the proprioception with

‘Marmara Visual Auditory Joint Education Device (MarvaJED)’, the kinesiophobia with ‘Tampa Kinesiophobia Scale (TKS), the satisfaction of the treatment with ‘Visual Analog Scale (VAS)’.

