**Statistical Analysis Plan (SAP)**

**(Pages 6 – 7)**

**April 8, 2019**

## **Statistical Analysis Plan (SAP)**

The statistical program Statistical Package for Social Sciences (SPSS) Version 11.5 (SPSS Inc., Chicago, IL, USA) will be used in the data analysis of the study. The p value of  $p < 0.05$  will be considered to be statistically significant in the data analysis. The initial demographic characteristics (age, boy, body weight) of all patients included in the study will be calculated.

‘Shapiro-Wilks Test’ will be used to investigate the appropriateness of the variables to normal distribution. ‘t-test’ will be used to compare the parameters of normal distribution in order to investigate the efficacy studies before and after the treatment; ‘Wilcoxon Test ‘ will be used to compare the parameters that do not comply with normal distribution.

**The Effectiveness of Game-Based Virtual Reality Approach in Patients with  
Subacromial Impingement Syndrome**

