### SPORTS/PERFORMING ARTS MODULE (OPTIONAL)

The following questions relate to the impact of your arm, shoulder or hand problem on playing *your musical instrument or sport or both*. If you play more than one sport or instrument (or play both), please answer with respect to that activity which is most important to you.

Please indicate the sport or instrument which is most important to you: \_\_\_\_\_

I do not play a sport or an instrument. (You may skip this section).

Please circle the number that best describes your physical ability in the past week. Did you have any difficulty:

	NO DIFFICULTY	MILD DIFFICULTY	MODERATE DIFFICULTY	SEVERE DIFFICULTY	UNABLE
1. Playing your instrument or sport in your usual way?	1	2	3	4	5
2. Playing your musical instrument or sport because of arm, shoulder or hand pain?	1	2	3	4	5
3. Playing your instrument or sport as well as you would like?	1	2	3	4	5
4. Spending your usual amount of time practising or playing your instrument or sport?	1	2	3	4	5

**Scoring the optional modules:** add up the assigned values for each response;

Divide by 4 (number of items); subtract 1; multiply by 25.

An optional module score may not be calculated if there are any missing items.

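### Does the DASH formula in Annex 2 put a primary outcome on the wrong scale?

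*Combined protocol and SAP*

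**What the plan says.** Table 1 in the protocol's Evaluations section lists disability as a primary outcome, measured by "The Disabilities of the Arm, Shoulder and Hand (DASH) Questionnaire". The questionnaire is reproduced in Annex 2. Below its last item stands the main-score rule, which the text shows as a fraction: "sum of n responses})-1)}{n} \times 25$ (where n is the number of completed responses". The next line limits missing data: "A DASH score may not be calculated if there are greater than 3 missing items".

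The rule for the optional work and sports/performing arts modules, on the same form, is given in words: "Divide by 4 (number of items); subtract 1; multiply by 25".

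The SAP names the software, the significance level, a normality check, and a t-test or Wilcoxon test "in order to investigate the efficacy studies before and after the treatment". It gives no scoring rule or range for DASH, or for any other outcome.

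**The concern.** Subtracting 1 from a sum of about 30 responses does almost nothing. Subtracting 1 from their mean moves a 1-to-5 scale to 0-to-4, which multiplication by 25 then stretches to 0-to-100. The fraction as transcribed does the first, and the module rule does the second. Someone who built the scoring sheet from the transcribed fraction alone would report every DASH level about 24 points too high. A patient with no difficulty on any item would score 24, and one answering 3 throughout would score 74 where the module order gives 50. Reported baseline and post-treatment means would then not be comparable with scores on a 0-to-100 scale. The SAP contains nothing on DASH scoring that would catch this.

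**Working it through.** **Inputs (all from Annex 2).**
- Item count: 30 rows are printed. The number 17 appears twice and 19 is absent (the row after the second 17 is "18 Recreational activities in which you move your arm freely"), but the count is still 30.
- Responses: 1 to 5 on every item.
- Completed items n: 27 to 30, since at most 3 may be missing.

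The documents state no DASH range, so there is no figure of theirs to reproduce. The 0-to-100 range used here is inferred from the module rule and the 1-to-5 responses.

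**Formulas**, with S the sum of the n responses:
- Literal order: L = (S − 1)/n × 25
- Module order applied to the main score: M = (S/n − 1) × 25
- Difference: L − M = 25 − 25/n, which does not depend on S

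**Range at n = 30.**
- All 1s, S = 30: L = 29/30 × 25 = 24.17; M = 0
- All 3s, S = 90: L = 89/30 × 25 = 74.17; M = 50
- All 5s, S = 150: L = 149/30 × 25 = 124.17; M = 100

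**Range and shift by n.**

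| n | L, all 1s | L, all 5s | M | Shift |
|---|---|---|---|---|
| 30 | 24.17 | 124.17 | 0 to 100 | 24.17 |
| 29 | 24.14 | 124.14 | 0 to 100 | 24.14 |
| 28 | 24.11 | 124.11 | 0 to 100 | 24.11 |
| 27 | 24.07 | 124.07 | 0 to 100 | 24.07 |

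**Effect on changes.** If a patient answers the same number of items at both visits, the shift cancels exactly. The worst case is 30 items at one visit and 27 at the other: 25/27 − 25/30 = 0.093 points. One response step on a complete form is worth 25/30 = 0.83 points, so the worst distortion is one ninth of a step. The same bound holds for a difference between two group means at one visit. A between-group difference in mean change could move by at most 2 × 0.093 = 0.19 points, and only if every patient in one group went from 30 to 27 answered items and every patient in the other went from 27 to 30.

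**Effect on the tests.** A paired t-test and a Wilcoxon signed-rank test use only the within-patient differences. The Shapiro-Wilk statistic does not change when a constant is added.

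**Which order is meant.** Three features point to division first:
- The outer brackets around the sum minus 1 are redundant if the whole expression sits over n. They are needed if only the sum does.
- The module rule uses the same response scale, the same subtraction of 1 and the same multiplier, and states the order in words.
- Under the literal order, patients with the same mean response but different n get slightly different scores, which defeats the purpose of dividing by the completed count. Under the module order they get the same score.

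The same line also has the word symptom split in two, which shows that the page was not read cleanly.

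**The case for a change.** The case for a change is that a real misprint cannot be excluded. The text alone does not show where the fraction bar ends on the source page, the form is the only place with a main-score rule, and the outcome is primary. A 0-to-100 range check would be weak protection. At n = 30 the literal score first exceeds 100 at S = 122 (121/30 × 25 = 100.83, where the module order gives 76.67). Sums from 30 to 121, which are 92 of the 121 possible, would therefore pass. A line in the SAP and a two-pattern test of the scoring sheet would cost almost nothing.

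The arithmetic stands, but it does not show a defect in the plan. The 92 of 121 counts possible sums equally and is not a share of patients, since the documents give no DASH distribution. The literal rule also leaves its own sign, a floor of about 24 that even a symptom-free patient could not go below. The intended order can be recovered from the form itself. The SAP gives scoring rules for no outcome, so repeating this one there would be a matter of presentation. The item numbering is a clerical slip: the formula uses the sum and the count, and neither depends on the printed numbers.

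**Conclusion.** No change to the plan follows. The text as read would give about 24 to 124 where the module order gives 0 to 100. That reading depends on the layout of one machine-read fraction, and the form's own brackets and module rule favour the ordinary order. If the literal order had been used, DASH levels would be 24.07 to 24.17 points too high. Before-after changes would be off by at most 0.09 points, and the planned tests would be essentially unaffected. No DASH cut-off or percentage-change endpoint in the documents would turn the shift into a different result.

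This rests on two assumptions: that 0 to 100 is the intended range, which the documents imply but do not state, and that whoever scores the form looks at the original page or follows the module order. The second is ordinary practice when a questionnaire is set up for analysis. Confidence that the source page carries a true misprint is low.

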## DISABILITIES OF THE ARM, SHOULDER AND HAND – British English

### WORK MODULE (OPTIONAL)

The following questions ask about the impact of your arm, shoulder or hand problem on your ability to work (including home-making if that is your main work role).

Please indicate what your job / work is: \_\_\_\_\_

I do not work (you may skip this section).

Please circle the number that best describes your physical ability in the past week. Did you have any difficulty:

	NO DIFFICULTY	MILD DIFFICULTY	MODERATE DIFFICULTY	SEVERE DIFFICULTY	UNABLE
1. Doing your work in your usual way?	1	2	3	4	5
2. Doing your usual work because of arm, shoulder or hand pain?	1	2	3	4	5
3. Doing your work as well as you would like?	1	2	3	4	5
4. Spending your usual amount of time doing your work?	1	2	3	4	5

### SPORTS/PERFORMING ARTS MODULE (OPTIONAL)

The following questions relate to the impact of your arm, shoulder or hand problem on playing *your musical instrument or sport or both*. If you play more than one sport or instrument (or play both), please answer with respect to that activity which is most important to you.

Please indicate the sport or instrument which is most important to you: \_\_\_\_\_

I do not play a sport or an instrument. (You may skip this section).

Please circle the number that best describes your physical ability in the past week. Did you have any difficulty:

	NO DIFFICULTY	MILD DIFFICULTY	MODERATE DIFFICULTY	SEVERE DIFFICULTY	UNABLE
1. Playing your instrument or sport in your usual way?	1	2	3	4	5
2. Playing your musical instrument or sport because of arm, shoulder or hand pain?	1	2	3	4	5
3. Playing your instrument or sport as well as you would like?	1	2	3	4	5
4. Spending your usual amount of time practising or playing your instrument or sport?	1	2	3	4	5

**Scoring the optional modules:** add up the assigned values for each response;

Divide by 4 (number of items); subtract 1; multiply by 25.

An optional module score may not be calculated if there are any missing items.

# Assessment of Quality of Shoulder Function- Constant Murley Score

## Patient-based Questionnaire

Date: .....

PATIENT'S NAME: ..... PATIENT NUMBER: .....

D.O.B.: ..... SIDE: RIGHT /LEFT

We would be grateful if you could take a few minutes to fill in this questionnaire. It is an essential part of our evaluation of the results of our treatment and surgery. It ultimately improves the quality of service we provide to you. **PLEASE COMPLETE THE FORM BY CIRCLING THE MOST APPROPRIATE RESPONSE.**

### A. PAIN

A1. Do you have pain in your shoulder during **normal** activities? (Please circle the most appropriate response)

1. NO PAIN      2. MILD PAIN      3. MODERATE PAIN      4. SEVERE PAIN

A2. LEVEL OF PAIN

If 0 means no pain and 15 means the worst pain you can have, **please circle the number** which describes your shoulder pain when you are doing **normal** activities:

☺ 0 1 2 3 4 5 6 7 8 9 10 11 12 13 14 15 ☹

NONE      MILD      MODERATE      SEVERE      UNBEARABLE

### B. FUNCTION (please circle the most appropriate response)

B1. Does your shoulder limit your occupation or daily living?

1. NO OR VERY SLIGHTLY      2. MODERATE LIMITATION      3. SEVERE LIMITATION

B2. Are your leisure and recreational activities limited by your shoulder?

1. NO OR VERY SLIGHTLY      2. MODERATE LIMITATION      3. SEVERE LIMITATION

B3. Does your shoulder disturb your night sleep?

1. NO      2. SOMETIMES      3. YES

B4. What level can you use your arm for **reasonable painless** movement?

1. WAIST      2. CHEST      3. NECK      4. EAR      5. ABOVE HEAD

B5. On a scale of 0 to 10, where 0 is **not satisfied** and 10 is **very satisfied**, how satisfied are you with your shoulder? (Circle the correct number)

☹ 0 1 2 3 4 5 6 7 8 9 10 ☺

**C. WHAT IS YOUR OCCUPATION?** .....

C1. How well can you perform your occupation? **(Please circle the most appropriate response)**

1. EASILY      2. WITH LITTLE DIFFICULTY      3. WITH MODERATE DIFFICULTY  
4. WITH EXTREME DIFFICULTY      5. NOT AT ALL

C2. What are your two main sporting/leisure activities?  
.....

C3. How well can you perform these activities? **(Please circle the most appropriate response)**

1. EASILY      2. WITH LITTLE DIFFICULTY      3. WITH MODERATE DIFFICULTY  
4. WITH EXTREME DIFFICULTY      5. NOT AT ALL

=====

**D. POSTOPERATIVE QUESTIONS** - only complete this section if you have had an operation

[Operation: ..... Date of operation:.....]

D1. How do you feel **now**, following your operation?  
**(Please circle the most appropriate response)**

1. MUCH BETTER      2. BETTER      3. SAME      4. WORSE

D2. Have you **now** **(Please circle the most appropriate response)**

1. Returned to the same occupation?  
2. Returned to the same occupation but with decreased level of activity (due to the shoulder)?  
3. Changed occupation due to the shoulder?  
4. Stopped working altogether because of your shoulder?

D3. If you have changed occupation, what job do you do now?:  
.....

D4. Have you **now** **(Please circle the most appropriate response)**

1. Returned to the same level of activity in the same sport?  
2. Returned to a decreased level of activity in the same sport (because of the shoulder)?  
3. Changed sports because of the shoulder?  
4. Stopped playing sports altogether because of the shoulder?

D5. If you have changed sports, what have you changed to?  
.....

**E. Range of Motion**

Copy the movements the model is performing – it may be useful to perform this exercise in front of a mirror.

Starting from left to right in each row

- **Tick the box** (below each photograph) if you are **able to perform the action**
- **Leave the box blank** if you **cannot perform** the action

**F. Strength**

Look at the two photographs below. Try to hold your arm in this position for 3 seconds each time carrying weights in the plastic bag.

Please use as weights within the plastic bag:

- **Bags of sugar**
- and/or
- **Filled plastic bottles of milk** (may be filled with water)
- and/or
- **Whatever is available for you with known weight**

Please record in the spaces below what was **the maximum weight** in kilograms (or pounds) or litres (or pints) that you **were able to hold in this position for 3 seconds** for each arm.

Seen from the front

seen from above

The maximum weight that I was able to hold in this position for 3 seconds:

Right Arm:		Kilograms/Litres	Left Arm:		Kilograms/Litres
Right Arm:		Pounds/Pints	Left Arm:		Pounds/Pints

**G. COMMENTS**

The space below is for any further comments you would like to make.

Thank you for filling in this questionnaire.

## Assessment of Kinesiophobia - Tampa Kinesiophobia Scale (TKS)

### Tampa Scale for Kinesiophobia (Miller , Kori and Todd 1991)

- 1 = strongly disagree  
 2 = disagree  
 3 = agree  
 4 = strongly agree

1. I'm afraid that I might injury myself if I exercise	1	2	3	4
2. If I were to try to overcome it, my pain would increase	1	2	3	4
3. My body is telling me I have something dangerously wrong	1	2	3	4
4. My pain would probably be relieved if I were to exercise	1	2	3	4
5. People aren't taking my medical condition seriously enough	1	2	3	4
6. My accident has put my body at risk for the rest of my life	1	2	3	4
7. Pain always means I have injured my body	1	2	3	4
8. Just because something aggravates my pain does not mean it is dangerous	1	2	3	4
9. I am afraid that I might injure myself accidentally	1	2	3	4
10. Simply being careful that I do not make any unnecessary movements is the safest thing I can do to prevent my pain from worsening	1	2	3	4
11. I wouldn't have this much pain if there weren't something potentially dangerous going on in my body	1	2	3	4
12. Although my condition is painful, I would be better off if I were physically active	1	2	3	4
13. Pain lets me know when to stop exercising so that I don't injure myself	1	2	3	4
14. It's really not safe for a person with a condition like mine to be physically active	1	2	3	4
15. I can't do all the things normal people do because it's too easy for me to get injured	1	2	3	4
16. Even though something is causing me a lot of pain, I don't think it's actually dangerous	1	2	3	4
17. No one should have to exercise when he/she is in pain	1	2	3	4

### Assessment of satisfaction after the treatment

- How satisfied are you with the decrease of pain at the end of treatment?

0.....5.....10  
(Not satisfied at all) (Very satisfied)

- How satisfied are you with your functionality at the end of treatment?

0.....5.....10  
(Not satisfied at all) (Very satisfied)

- How satisfied are you with all of your treatment?

0.....5.....10  
(Not satisfied at all) (Very satisfied)

- How satisfied are you with your physiotherapist?

0.....5.....10  
(Not satisfied at all) (Very satisfied)

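### Treatment satisfaction, a primary outcome, is scheduled at baseline although its form fits only post-treatment use, and the SAP's before/after comparison, on its natural reading, cannot be run on one value per patient

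*Combined protocol and SAP*

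**What the plan says.** **Protocol, Evaluations.** One schedule sentence covers every outcome: "A Physiotherapist will applying the following evaluation parameters at the baseline, and at the end of 4-weeks treatment program". Table 1 then lists nine primary outcome measures. The last is "Satisfaction of the Treatment", measured by visual analogue scale, and no row is exempted from the baseline assessment.

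**Annex 2, satisfaction form.** The form is headed "Assessment of satisfaction after the treatment" and has four 0–10 items. The first asks "How satisfied are you with the decrease of pain at the end of treatment", the second asks about functionality at that same time, the third asks "How satisfied are you with all of your treatment", and the fourth asks about the physiotherapist.

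**SAP.** Variables are checked for normality. For normally distributed ones a t-test is planned "in order to investigate the efficacy studies before and after the treatment". The Wilcoxon test "will be used to compare the parameters that do not comply with normal distribution". The SAP does not mention the two groups.

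**Protocol, Randomization and Hypothesis.** Patients are randomised to two groups. The hypothesis concerns what virtual reality exercises add for disability, range of motion and pain. Satisfaction is not in it.

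**The concern.** A before/after analysis needs a value before treatment. The satisfaction form asks about results that do not yet exist at baseline, so it yields one usable value per patient. If the SAP is followed on its natural reading, a declared primary outcome has no usable test, and the randomised contrast, which is the only sound basis for attributing a difference in satisfaction to the virtual reality exercises, is not used for it. The analyst would then have to choose the comparison, and which of four items to compare, after the data are in.

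There is also a practical reason to deal with satisfaction by name. A sponsor who repairs the SAP by adding a between-group analysis of change scores, or one adjusted for baseline, would still leave this outcome out.

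**Working it through.** The documents state no sample size, SD, effect size or power, so there is no figure of theirs to reproduce. The check sets the measurements available against those each comparison needs.

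**Step 1. Count the primary outcomes (Table 1).** Range of motion, pain, disability, shoulder function, muscle strength, pain threshold, proprioception, kinesiophobia and satisfaction: 9.

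**Step 2. Count usable satisfaction values per patient.** The Evaluations section implies 2 (baseline and 4 weeks). On the form, items 1 and 2 refer explicitly to the end of treatment and item 3 to the treatment as a whole, so 3 of the 4 items presuppose treatment received. Item 4 stands under the same post-treatment heading. Usable values: 1.

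**Step 3. Look for a substitute baseline.** Annex 2 has one other 0–10 satisfaction item that could be answered before treatment, item B5 of the Constant-Murley form: "how satisfied are you with your shoulder". It concerns the shoulder and not the treatment, and it belongs to a different outcome. It does not supply the missing value.

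**Step 4. Count outcomes with a stated between-group test.** The SAP mentions no groups: 0 of 9.

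**Step 5. Coverage of each type of comparison.** The other 9 − 1 = 8 outcomes are scheduled at both times, and nothing in the documents restricts them to one.

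| Comparison | Values needed per patient | Primary outcomes covered |
|---|---|---|
| Before/after (SAP, natural reading) | 2 | 8 of 9 |
| Between groups, change score or baseline-adjusted | 2 | 8 of 9 |
| Between groups, 4-week score | 1 | 9 of 9 |

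Only the last row is a comparison that a post-treatment outcome can enter. The middle row is not in the plan. It shows that a general repair need not reach satisfaction.

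**The case against.** Several objections have force.

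- **The SAP is ambiguous.** It does not say whether the t-test is paired or independent, or whether the Wilcoxon test is signed-rank or rank-sum, and the Wilcoxon clause does not itself repeat the before/after purpose. The wording could loosely mean comparing the groups at each time point, in which case the 4-week satisfaction score is testable. This stands in part. A reader might infer that the SAP rules out any test of satisfaction. The documents do not go that far, since no usable test is clearly stated but none is excluded. The within-patient reading is still the natural one, because the purpose given is before/after and no groups are named.
- **The timing is not settled.** A reader might take post-treatment-only measurement as an established fact of the design. The Evaluations section says otherwise. What the documents show is a conflict between the schedule and the form.
- **This is a sub-case.** The unused randomised contrast affects all nine outcomes, so that harm should not be counted again here. That stands. What is particular to satisfaction is the missing baseline.
- **The choice of item is open.** A reader might infer that the third item is the one to test. It is the closest match to the Table 1 label, but nothing in the documents ranks it above the others or above a composite. Nor is the lack of an item rule peculiar to satisfaction: Annex 2 has two pain items and ten movements with no selection rule either.
- **Satisfaction could be made secondary or descriptive.** That is open to the sponsor. It would still have to be written down.

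**Conclusion.** The point holds at modest weight. The schedule in the Evaluations section and the Annex 2 form conflict and must be reconciled. On the natural reading of the SAP, the only planned comparison cannot be computed for 1 of 9 declared primary outcomes, and a between-group test is stated for none of the 9.

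The conclusion rests on two readings: that the form can be answered meaningfully only after treatment, which its heading and items support, and that the SAP's comparison is within patients, which is likely but not certain. It does not touch the outcomes named in the hypothesis, so a reader should not infer that the trial's main question is undermined by this point alone. Nothing can be said about the power of a 4-week comparison, because no sample size or SD is given.

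**What to change.** **Protocol, Evaluations.** State that treatment satisfaction is assessed at 4 weeks only, which brings the schedule into line with the form.

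**SAP.** Add a paragraph to this effect:

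> *Treatment satisfaction has no baseline value. The 4-week score on [item or composite named by the sponsor] will be compared between Group II and Group I with an independent t-test, or the Mann-Whitney test if the data are non-normal, and the between-group difference will be given with its 95% CI (Hodges-Lehmann difference with the Mann-Whitney test). The remaining items will be reported descriptively by group.*

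The sponsor should name the item or composite before the data are seen. The third item, "How satisfied are you with all of your treatment", is the natural candidate because it best matches the Table 1 label.

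**Cost.** One phrase in the protocol and one short SAP paragraph, with no new data or visits. If a general between-group analysis is added to the SAP, a single clause for this post-treatment outcome is enough. The items not chosen get no formal test, which is a small loss. The change does not settle multiplicity across the nine primary outcomes, which needs its own decision.
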